- Require a knee stabilizing device (i.e. Knee-Ankle Foot Orthosis or Knee Orthosis) to perform daily activities
- Surgery on study limb anticipated in the next 6 months
- Medical or psychological conditions that would preclude functional testing (ex. severe traumatic brain injury, heart condition, clotting disorder, lung condition, stroke, vestibular disorder)
- Nerve, muscle, bone, or other condition limiting function of the contralateral extremity
- BMI greater than 45
- Visual or hearing impairment that limit walking ability or limit the ability to comply with instructions given during testing
- Pregnancy

Design and Methods:

Personal/demographic (age, race, education, and self-efficacy, gender, ethnicity, date and mechanism of injury, surgical history, and current device, if any), injury characteristics (injury description and characteristics, fracture classification, and surgical history), and anthropometric information (height, weight, dominant leg, leg length, shoe length and width) will be used to characterize the cohort. Multiple outcomes measures will be used to characterize patient-centric outcomes and evaluate device function and participant outcomes.

The Four Square Step Test (4SST) uses a 1 inch pipe placed on the floor in the shape of a Maltese cross. Participants are instructed to begin in the back left quadrant and move 1) forward, 2) right, 3) backward, 4) left, then to move in the reverse direction back to the original square as fast as possible. During the *Sit to Stand 5 Times (STS5)* participants start sitting with their arms folded across their chest and their back against a chair. Participants are then instructed to stand up and sit down 5 times as fast as possible, avoiding touching their back to the chair during each repetition. During the *Self-Selected Walking Velocity (SSWV)* test participants are instructed to walk at their “normal comfortable” pace for a 10 m distance. Participants are timed as they walk in the middle 6m, the first and last 2m are not timed to account for participants speeding up and slowing down. During the *10 Meter Shuttle Run (SR)* participants are instructed to move as fast as possible for 10 meters, pick up a wooden block, return it to the ground behind the start line, and then turn around and repeat the procedure to pick up a second block. In the *Timed Stair Ascent (TSA)* participants are instructed to ascend a flight of 12 steps as quickly and safely as possible while contacting every step.

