Aim 1 requires a sample size of 59 participants to provide greater than 80% power (2-sided test) at an alpha level of 0.05 to detect a 10% difference between study orthotic devices (Aim 1) in 4SST and in SSWV. These values are based on published mean and standard deviation data (4SST=5.8±1.8 seconds, SSWV=1.50±1.8 seconds) for use of a dynamic orthotic device similar to the Reaktiv in individuals with similar injury characteristics, and assuming a correlation between measures within participants of 0.65.

Aim 2 will be adequately powered based on the results of previously published data. A total of 27 and 25 participants will be necessary for the 4SST and SSWV, respectively, to detect a significant difference with 80% power (2-sided test), an alpha level of 0.01, and 20% non-completion.

A formal sample size calculation for Aim 3 has not been performed because it is exploratory and requires prior knowledge of an expected odds ratio and proportion of participants who select each preference option. The rule of thumb is to have a minimum sample of 10 participants per independent variable in the model or a ratio of 10:1 for participants to variables. As such, we estimate we would have power to include up to 3 predictors.

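### The printed SSWV inputs give about 12% power at 59 participants for a 10% difference, not the stated power above 80%

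*Combined protocol and SAP*

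**What the plan says.** The Aim 1 paragraph of the Power Analysis section states: "Aim 1 requires a sample size of 59 participants to provide greater than 80% power (2-sided test) at an alpha level of 0.05". The target is to "detect a 10% difference between study orthotic devices (Aim 1) in 4SST and in SSWV". The inputs are "4SST=5.8±1.8 seconds, SSWV=1.50±1.8 seconds", attributed to published data on a device similar to the Reaktiv, with an assumed within-participant correlation of 0.65. The Analysis Methods section names the paired t-test for the Aim 1 comparison of the two devices.

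The Design and Methods section describes SSWV as a velocity test over a 10 m walk at the participant's usual pace: "Participants are timed as they walk in the middle 6m". No other part of the document gives a different SSWV mean or SD.

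**The concern.** The SSWV entry looks wrong before any calculation is done:

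- SSWV is a velocity, but it is given in seconds.
- Its SD (1.8) exceeds its mean (1.50), for a quantity that cannot be negative.
- Its SD and unit are the same as those of the 4SST entry printed just before it.
- It cannot be reread as a time. Covering the 6 m timed zone in 1.50 s means 6 / 1.50 = 4 m/s, which is not a comfortable walking pace.

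This entry feeds directly into the calculation. SSWV is one of only two outcomes used to justify the sample size, and the power claim covers both. If the inputs do not support the claim, a reader cannot tell what size of SSWV difference the trial was planned to detect.

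**Working it through.** **Inputs.** All come from the SAP: n = 59 participants, each measured with both devices; two-sided alpha 0.05; difference of 10% of the mean; correlation rho = 0.65; paired t-test; 4SST 5.8 (SD 1.8); SSWV 1.50 (SD 1.8).

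**Formulas.**
- SD of paired differences: SD_d = SD × sqrt(2 × (1 − rho)).
- Noncentrality: delta / SD_d × sqrt(n), with n − 1 degrees of freedom.
- Power comes from the noncentral t distribution, counting both tails.

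**SD of differences.** The two printed SDs are equal, so both outcomes share one value: 1.8 × sqrt(2 × 0.35) = 1.8 × sqrt(0.70) = 1.506.

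**4SST, the half that can be reproduced.**
- delta = 0.10 × 5.8 = 0.58
- standardised difference = 0.58 / 1.506 = 0.385
- noncentrality at n = 59: 0.385 × sqrt(59) = 2.96
- power at 59 = 82.9%, and 80% is first reached at 55 pairs

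The claim of more than 80% holds here, which supports this as the calculation the plan intended.

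**SSWV, as printed.**
- delta = 0.10 × 1.50 = 0.15
- standardised difference = 0.15 / 1.506 = 0.0996
- noncentrality at n = 59: 0.0996 × sqrt(59) = 0.765
- power at 59 = 11.7% (normal approximation 11.6%)
- participants needed for 80% power = 794 (normal approximation 792)
- difference detectable at 59 with 80% power = 0.56, and 0.56 / 1.50 is about 37% of the mean

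**Other readings, keeping the SD at 1.8.**

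| Reading | SSWV power at n = 59 |
|---|---|
| One-sided alpha 0.05 | 18.7% |
| 1.8 taken as the SD of the difference | 9.6% |
| rho = 0.90 | 29% |
| rho = 0.95 | 51% |
| rho = 0.98 | 88% |

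Power reaches 80% only at a correlation of about 0.975, against the stated 0.65.

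**What SD would make the claim true?** With n = 59, delta 0.15 and rho 0.65, the largest SD giving 80% power is 0.483, which is 0.483 / 1.50 = 32% of the mean. The SDs below are assumptions for illustration, not values from the documents.

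| Assumed SSWV SD | n for 80% power | Power at n = 59 |
|---|---|---|
| 0.18 | 10 | >99.9% |
| 0.30 | 24 | 99.5% |
| 0.40 | 42 | 92% |

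**The case against.** The strongest reply is that this is a misprint and not a power failure. If 1.8 was copied across from 4SST, then 11.7% and 794 describe no real trial. The Aim 2 paragraph gives indirect support. It asks for 25 participants for SSWV at alpha 0.01, 80% power and 20% non-completion, so 25 × 0.8 = 20 completers. If the Aim 1 SD of 1.8 and correlation of 0.65 applied there, the difference to be detected would be about 1.26, or 1.26 / 1.50 = 84% of the mean, which is implausible. The Aim 2 inputs are not printed, so this is suggestive only.

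It can also be said that 4SST alone supports 59, that the planned paired t-test is unaffected, and that a null SSWV result would be read from its observed confidence interval and not from a planning SD.

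Much of this stands. A copying error is the likelier explanation, the point does not show that the trial is underpowered for SSWV, and a null result would remain interpretable through its interval. None of it makes the printed claim follow from its inputs. The plan asserts power for both outcomes, and the document contains no SSWV SD from which the second assertion can be checked.

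**Conclusion.** The concern holds. As written, the SSWV part of the Aim 1 power statement is contradicted by its own inputs: 11.7% against a claim of more than 80%, and 794 participants needed against 59. The result uses only the SAP's printed values and its named test, and no reasonable alternative reading rescues it. The 4SST part is sound at 82.9% with 59 completed pairs, so the total of 59 does not fall with the SSWV figure. Whether SSWV is in fact adequately powered is unknown from the documents. It is if the true SD is about 0.48 or less in the units of the mean, taking the mean of 1.50 and the correlation of 0.65 as given. The statement must be corrected because a wrong figure stands behind a stated power.

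**What to change.** Check the SSWV mean, SD and unit against the published source and replace the entry, with SSWV in a velocity unit. Rerun the paired calculation and report power separately: 82.9% for 4SST at 59 completed pairs, and the recomputed figure for SSWV. If 1.8 proves to be the SD that was actually used, withdraw the SSWV power claim and give the detectable difference at 59 (about 37% of the mean on the printed inputs).

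The cost is one corrected entry and one rerun. No change to the design, sample size or analysis follows if the true SD is about 0.48 or less.

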Impairment, biomechanical, and orthosis data will be used to compare between conditions and characterize limb and CDO function, to provide insight in a manner not commonly found in comparative studies. Impairment data will include *ankle range of motion and stiffness* which will be assessed using the Iowa Ankle Range of Motion device that utilizes a handheld force gauge and digital inclinometer. *Ankle strength* will be assessed using the Standing Heel-Rise Test where participants will perform as many standing heel-rises as they can. *Knee range of motion and strength* will be assessed using a goniometer aligned with the femur and tibia and Manual Muscle Testing as participants are seated with their legs dependent and their knees flexed about 90 degrees. Biomechanical data will include *ground reaction force and motion capture* data that will be used to evaluate the motion and loading of the lower limb as participants walk on an over ground walkway at self-selected speed and a controlled speed based on leg length.

Statistical Analysis Plan:

Analysis Methods:

Aim 1: We will use paired t-tests to compare continuous measures between use of the Reaktiv and PhatBrace. Data that are not normally distributed will be log-transformed and their distributions re-evaluated. If distributions are not normalized using this transformation, we will utilize the Wilcoxon Signed Rank Test in place of the paired t-test.

Aim 2: A series of paired t-tests will be used to test for significant differences in continuous measures between 1) each study orthotic device and the standard of care and 2) between each study orthotic device and no brace. We will utilize a Bonferroni-Holm correction to account for multiple comparisons. Data that are not normally distributed will be log-transformed. In cases where log transformation does not normalize distributions, analyses will be completed using the Wilcoxon Signed Rank Test.

Aim 3: We will use multinomial logistic regression to evaluate the relationship between the primary device preference and participant baseline characteristics such as age, height, weight, strength and motion, desired activity level, and physical ability as determined in the no device condition. If complete or quasi-complete separation occurs, due to low selection of a study orthotic device or standard of care, the categories will be collapsed to the two remaining options and logistic regression will be utilized.

Power Analysis:

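### The Aim 3 statement of power for up to 3 predictors is unsupported: the 10:1 rule cannot establish power, gives 3 at no sample size in the plan, and does not fit a three-category model

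*Combined protocol and SAP*

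**What the plan says.** In the combined protocol and SAP, Analysis Methods, Aim 3: "We will use multinomial logistic regression to evaluate the relationship between the primary device preference and participant baseline characteristics". Preference is a ranking of three conditions (Device A, Device B and standard of care, per Design and Methods), so the model has two logits. About seven baseline characteristics are listed as examples of predictors. The plan falls back to a binary logistic model only if complete or quasi-complete separation occurs.

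The Power Analysis section says that no formal calculation was made for Aim 3, because the aim is exploratory and the calculation would need an expected odds ratio and the share of participants choosing each option. It then gives a rule of thumb, "a minimum sample of 10 participants per independent variable in the model or a ratio of 10:1 for participants to variables", and concludes from it that "we estimate we would have power to include up to 3 predictors". It does not say which sample size was divided by 10.

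The sample sizes in the same section are for the other aims: "Aim 1 requires a sample size of 59 participants", and, for Aim 2, "A total of 27 and 25 participants will be necessary for the 4SST and SSWV, respectively". The only loss rate is in the Aim 2 sentence: "an alpha level of 0.01, and 20% non-completion".

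**The concern.** Three things do not fit together.

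- The paragraph declines a power calculation for want of inputs and then asserts power. A participants-per-variable rule limits overfitting. It contains no effect size, no alpha and no outcome distribution, so it cannot produce power.
- The figure 3 is presented as following from the rule, but the rule does not give 3 at any sample size in the plan.
- The rule counts participants per variable. In a three-category multinomial model each one-df predictor carries two slopes, and the least-chosen option limits the information available to estimate them.

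At stake is how the Aim 3 results are read. A non-significant predictor could be taken as evidence of no association, and odds ratios from a thin model could be taken at face value, because the plan said the model had power. Aim 3 concerns factors associated with device preference, in a study intended to inform clinical practice.

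**Working it through.** **1. The plan's own rule.** Predictors = floor(N / 10), tried with each N that the plan gives or that follows from its loss rate.

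| N | Source | N/10 | Predictors allowed |
|---|---|---|---|
| 59 | Aim 1 | 5.9 | 5 |
| 47 | 59 × 0.8 (20% loss, stated only for Aim 2) | 4.7 | 4 |
| 74 | 59 / 0.8 (same assumption, inflating) | 7.4 | 7 |
| 27 | Aim 2, 4SST | 2.7 | 2 |
| 25 | Aim 2, SSWV | 2.5 | 2 |

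Three predictors correspond to N = 30 to 39. Reaching that from 59 needs a loss between 1 − 39/59 = 34% and 1 − 30/59 = 49%, which is stated nowhere. The figure 3 is not reproduced.

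**2. Is 59 a fair base?** With the 4SST inputs in Power Analysis (mean 5.8, SD 1.8, 10% difference = 0.58, correlation 0.65), the SD of the paired difference is 1.8 × √(2 × 0.35) = 1.506. A paired t-test then needs 55 participants for 80% power, and 59 gives 82.9%. This agrees with the stated "greater than 80% power (2-sided test) at an alpha level of 0.05", so 59 is a usable N.

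**3. Counting slopes.** Three one-df predictors × two logits = 6 slopes, plus 2 intercepts. Ten participants per slope means 20 per predictor: 59/20 = 2.95, so 2; 47/20 = 2.35, so 2; 74/20 = 3.7, so 3.

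**4. Counting the least-chosen option.** Its size cannot exceed floor(59/3) = 19, or floor(47/3) = 15. Within one contrast there are three slopes: 19/3 = 6.3 participants per slope at best, or 15/3 = 5.0. Asking instead for 10 participants per predictor in the smallest category (the splits are assumptions, since the plan gives none):

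| Split | Smallest category, N = 59 | Predictors | Smallest category, N = 47 | Predictors |
|---|---|---|---|---|
| Equal thirds | 19.7 | 1 | 15.7 | 1 |
| 40/40/20 | 11.8 | 1 | 9.4 | 0 |
| 45/45/10 | 5.9 | 0 | 4.7 | 0 |

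**5. Illustration by simulation.** Assumed inputs: three predictors, one of them with an odds ratio of 2 per SD (log-odds ratio 0.69) on one contrast; a 2-df likelihood-ratio test; maximum-likelihood fit. The effect on the second contrast must also be assumed, and power depends strongly on it. With equal thirds and 600 trials per cell:

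| Second log-odds ratio | Power, n = 59 | Power, n = 47 |
|---|---|---|
| 0 | 55% | 47% |
| +0.35 | 43% | 40% |
| +0.69 | 56% | 48% |
| −0.69 | 93% | 86% |

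Across splits from equal thirds to 45/45/10 (400 trials per cell, Monte Carlo standard error at most √(0.25/400) = 2.5 percentage points), power ran from about 29% to 94%. The mean estimated log-odds ratio was above the true value in every cell, at 0.75 to 0.98. Against 0.69 that is 0.75/0.69 = 1.09 to 0.98/0.69 = 1.42, or roughly 10–40% too large.

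**The case against.** The best defence is that 3 is cautious. At N = 59 the stated rule allows 5, and at 47 it allows 4, so a reader who infers that the plan breaks its own rule at the Aim 1 sample size would be wrong. What stands against the plan is only that 3 cannot be derived, and that the rule is the wrong one for this model.

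The authors may have counted two slopes per predictor and rounded 59/20 = 2.95 up to 3. That is possible, but the text counts per independent variable, 2.95 falls short of 3, and the least-chosen option is still ignored.

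A reader might also infer that power is about 45–60%. The documents do not support that or any other single figure: it holds only for particular choices of the second contrast, and the documents give neither effects nor proportions. Nor does a less even split always lower power: at n = 59 with no effect on the second contrast, 40/40/20 gave 61% against 55% for equal thirds. The smallest category limits how many slopes can be estimated stably; it does not by itself fix power.

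Dividing 19 by all six slopes gives 3.2 participants per slope, which looks worse than 6.3. That is one counting convention, and nothing in the documents favours it. The figure of 47 completers borrows a loss rate stated only for Aim 2.

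Finally, Aim 3 is labelled exploratory, the sample size does not depend on it, and there is a binary fallback. These limit the consequence but do not make the power statement true. The fallback acts only on separation: in simulated trials with no effect on the second contrast, apparent separation arose in 0–4%, so inflated estimates would usually pass through it.

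**Conclusion.** The point holds, at minor severity. The power statement for Aim 3 has no basis in the plan, 3 does not follow from the cited rule at any N given, and the rule takes no account of two slopes per predictor or of the least-chosen option. These conclusions rest on the documents and simple arithmetic.

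The simulated range of power and the upward bias are illustrations. They rest on an assumed odds ratio, assumed splits, an assumed second contrast and, at n = 47, an assumed loss. They show that power could be low or high and that unpenalised estimates tend to be too large. They do not show that a three-predictor model is impossible to fit, or that the trial's overall sample size is wrong. A reader might also take the plan to call the Aim 3 model adequately sized. It makes no such statement; it claims power for up to three predictors, and that claim is what needs correcting.

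**What to change.** In Power Analysis, Aim 3, delete the statement of power and say that no power is claimed for this aim. State that the number of predictors will be set from the observed size of the smallest preference category, counting two slopes per predictor, and give the N used. In Analysis Methods, Aim 3, specify a Firth-type penalised multinomial fit, with estimates reported with 95% confidence intervals as hypothesis-generating. Do not insert a replacement power figure: the plan has no odds ratio or preference proportions to support one.

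The cost is SAP wording and a little more analysis work. The stated capability of Aim 3 becomes less favourable. No extra participants or data are needed.
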